The risks are the side effects associated with each drug. For prochlorperazine, this includes drowsiness, blurred vision, xerostomia, congestion, nausea, akathisia, tardive dyskinesia, NMS, and blood dyscrasias. For Benadryl include sedation, tiredness, sleepiness, dizziness, constipation, dry mouth, blurred vision, nausea, and loss of appetite. For normal saline, this

includes injection site swelling, redness, infection, venous thrombosis or phlebitis or hypervolemia. Personal benefits include intended reduction in headache symptoms and the satisfaction that the patient may be assisting investigators in determining a more effective headache treatment.

Interventions

After enrollment, each patient will be randomized either to the standard treatment arm to receive prochlorperazine 0.15 mg/kg up to 10 mg IV along with diphenhydramine 1mg/kg (up to 50 mg) IV and normal saline at 5 mL/h IV OR to the study arm to receive prochlorperazine along with diphenhydramine IV and normal saline at 20 mL/kg (up to 1000 mL) given IV over 1 hour. The diphenhydramine will be administered first, and immediately afterward the prochlorperazine will be administered. The patient will then be connected to normal saline on an IV pump and randomized to 5 cc over an hour or 20 cc/kg (maximum 1000 cc) over one hour. The IV bag and pump will be covered so that the patient will not know how much fluid they are receiving. Patients will undergo simple randomization to either the fluid bolus group or the control group. The treating physician will consult a folder that contains a list specifying the group assignment. Each row of the list corresponded to a patient, and will be covered by a small slip of opaque paper that will be removed at the time of enrolment to reveal the group assignment. This list was constructed at the beginning of the study using a random number generator by a research staff. Randomization in the pediatric ED and adult ED will be separate to ensure equal numbers of pediatric patients in both the experimental and control arms (blocking). Emergency providers will be instructed not to administer any rescue medications for at least 30 minutes.

Safety

After 30 minutes, the treating provider will be permitted to administer a “rescue medication” of their choice for further treatment. If there is an untoward event that requires the patient to know which IVF dose was administered, patient will unblinded and will not continue in the study.

Reportable Events

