Anticipated side effects are those listed on the manufacturer’s package insert and are treated as routine non-urgent or non-emergent events are not reportable events.

Adverse Events are those unanticipated side effects that require interventions or anticipated side effects that do not respond to intervention.

Serious Adverse Events are those side effects that require Advanced Life Support measures to control symptoms.

AEs and SAEs will be reported to the IRB within 5 days of the event.

Methods of Measurement

Enrolled patients will fill out a brief data collection form to include age, sex, race, phone number, and baseline headache severity using a 100-mm visual analog scale (VAS). Repeat headache severity scores will be measured at 30 and 60 minutes. Time zero begins immediately after complete administration of the study drug. Nausea (with a 100 mm VAS) and vomiting will also be assessed at these time intervals. The need for rescue medications will be extracted from the patient's chart at a later time.

Trained research assistants will call the patient 24-48 hours post-discharge by phone to ask if they are currently having a headache (yes or no) and to rate their current pain (0-10). If the patient is admitted, the patient will be approached in the hospital by an investigator or research assistant for follow up.

Outcome Measures

The primary outcome measure will be the difference in pain scores between the 5 cc over an hour and 20 mg/kg (up to 1000 cc) over an hour groups measured as the absolute difference between the means at 60 min. Secondarily, we will measure the difference between the rates of decline in pain scores, rate of admission, nausea scores, rate of vomiting, rate of use of additional medications for headache, and headache resolution with telephone follow up.

Privacy and Security

In order to protect the privacy of the research subjects and to maintain the confidentiality of data, all data will be managed only by trained research assistants or investigators and will be stored in the locked Emergency Medicine research offices and electronic data will be stored on a password protected computer in the locked Emergency Medicine research office. All research assistants and investigators are HIPAA- trained, CITI trained and credentialed by UMC IRB, and oriented to the study protocol.

Data Analysis:

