Assuming a SD of 22 (based on prior data from our institution), we calculated that we would need 45 patients in each group to find a clinically important difference in pain score reduction (13 mm) between groups at 60 min with at least 80% power and an alpha of 0.05.

The groups will be compared using a t -test on gender, race, and age; and a chi (with Yates correction)-squared test on severity of presenting headache, to determine if they are similar. The individual VAS measurements will be compared using a repeated measures analysis of variance (ANOVA) test.

REFERENCES

[1] R.B. Lipton, M.E. Bigal, M. Diamond, F. Freitag, M.L. Reed, W.F. Stewart, et al. Migraine prevalence, disease burden, and the need for preventive therapy. *Neurology*, 68 (2007), pp. 343–349

[2] B.W. Friedman, J. West, D.R. Vinson, M.T. Minen, A. Restivo, E.J. Gallagher. Current management of migraine in US emergency departments: an analysis of the National Hospital Ambulatory Medical Care Survey. *Cephalalgia*, 35 (2015), pp. 301–309

[8] Jones J, et al. Randomized double-blind trial of intravenous prochlorperazine for the treatment of acute headache. *JAMA*. 1989;261:1174-1176.

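### A patient told the fluid dose after an untoward event leaves the study, so outcomes may be lost after randomisation, possibly unequally by arm, and no analysis set is named

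*Combined protocol and SAP*

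**What the plan says.** Safety provides for an untoward event after which the patient has to be told the fluid dose. If the event "requires the patient to know which IVF dose was administered, patient will unblinded and will not continue in the study". The text does not separate the loss of blinding from the end of data collection.

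Three other places bear on how often this could happen and what it could remove:

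- **Risk/Benefit.** The saline risks are listed: the text "includes injection site swelling, redness, infection, venous thrombosis or phlebitis or hypervolemia". Under Interventions, the arms differ only in saline volume: 5 mL over an hour against 20 mL/kg, up to 1000 mL, over an hour.
- **Interventions.** Only the patient is blinded: "The IV bag and pump will be covered so that the patient will not know how much fluid they are receiving". The treating physician consults the allocation list, where each row "will be covered by a small slip of opaque paper that will be removed at the time of enrolment to reveal the group assignment".
- **Methods of Measurement.** Pain is self-rated at 30 and 60 minutes. Later, "Trained research assistants will call the patient 24-48 hours post-discharge by phone to ask if they are currently having a headache". Rescue medication use is taken from the chart afterwards.

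On analysis, Data Analysis gives the sample size ("we would need 45 patients in each group to find a clinically important difference in pain score reduction (13 mm) between groups"), baseline comparisons, and one sentence on the pain scores: "The individual VAS measurements will be compared using a repeated measures analysis of variance (ANOVA) test". It names no analysis set and does not say how a patient without a score, or a withdrawn patient, is treated.

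**The concern.** Leaving the study after randomisation for a reason that may depend on the treatment takes away randomisation's protection for the patients concerned. Here the reason is an untoward event for which the fluid volume matters. Because volume is the only planned difference between the arms, and hypervolemia is a listed saline risk, such events could plausibly differ by arm. If those patients also differ in pain from the patients who stay, the comparison of 60-minute means is shifted.

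Two outcomes are exposed. The 60-minute score is at risk only if the event comes before it. The 24-48 hour contact is at risk from any unblinding during the ED stay. Because no analysis set is named, the handling of such a patient could be settled after the data are seen.

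**Working it through.** **Inputs from the documents (Data Analysis).** SD 22, target difference 13 mm, 45 per group, alpha 0.05, power at least 80%. Sidedness is not stated; two-sided is used because it reproduces the stated size (a one-sided calculation gives 36).

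**The plan's own figure.** n = 2 × (1.960 + 0.842)² × 22² / 13² = 44.96, so 45 per group. Power at 45 is 80.04% by the normal approximation and 79.2% by the t-test. The stated size is reproduced.

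**Assumed inputs.** The documents give no event rate. Assume k = 1 or 2 patients are lost before the 60-minute score from one arm and none from the other. Assume their 60-minute pain would have differed by D = 10 or 20 mm, in either direction, from that of retained patients.

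**Bias.** The full arm mean is the retained mean plus (k/45) × D, so leaving these patients out shifts the arm mean by (k/45) × D. The standard error of the difference is 22 × √(2/45) = 4.64 mm. False-positive rates are for a two-sided t-test (noncentral t) with no true difference and the arm reduced by k.

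| k | D (mm) | Bias (mm) | Share of 13 mm | Bias / SE | False-positive rate |
|---|---|---|---|---|---|
| 1 | 10 | 0.22 | 1.7% | 0.05 | 5.03% |
| 1 | 20 | 0.44 | 3.4% | 0.10 | 5.10% |
| 2 | 10 | 0.44 | 3.4% | 0.10 | 5.10% |
| 2 | 20 | 0.89 | 6.8% | 0.19 | 5.40% |

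**Power at a true 13 mm difference (t-test).** It is 79.2% with 45 v 45 and 78.2% with 45 v 43 and no bias. With 45 v 43 and a 0.89 mm bias it is 72.3% (13 − 0.89) or 83.3% (13 + 0.89), depending on sign.

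**Offsetting losses.** With 2 lost in one arm and 1 in the other, D = 20 mm in each and of the same sign, the bias is 0.89 − 0.44 = 0.44 mm and the false-positive rate is 5.10% (44 v 43).

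**Later events.** If every event follows the 60-minute score, and scores already taken are kept, the primary bias is zero. For the telephone outcome, assume 20 of 45 in an arm (44.4%) still have a headache. If 2 are lost, the observed figure is 18/43 = 41.9% when both had a headache and 20/43 = 46.5% when neither did.

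**The case against.** **The rule may mean less than it seems to.** Not continuing in the study could mean stopping the study treatment only. The text does not say that the call is cancelled or that scores already taken are discarded, and rescue use comes from the chart. This stands as far as it goes: the text supports that outcomes may be lost, not that they are. Loss remains the natural reading, and nothing elsewhere in the document says otherwise.

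**Unequal loss is inferred.** The document does not connect hypervolemia with unblinding. The other listed saline risks could arise in either arm, since both have an IV line and a saline infusion, and drug side effects are common to both. This also stands. A reader might infer that the rule will remove mainly bolus patients and so favour one arm. The documents do not support that: they give neither a rate nor a direction.

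**It is rare and small.** The physician learns the assignment at enrolment, so staff need not break a code to manage an event; only an event that requires telling the patient counts. The 72.3% power figure belongs to one corner of the assumptions and one sign. This is accepted and sets the weight of the point.

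**Retained scores have their own bias.** Pain is self-rated and the patient is the only blinded party. If knowing the dose moved 2 of 45 scores by 10 mm, the arm mean would shift by (2/45) × 10 = 0.44 mm, which lies within the range computed for loss. A net reduction in bias is therefore not demonstrated. The case for retention is that all randomised patients stay in the comparison and the affected scores can be identified and tested.

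**The time window is unclear.** Time zero follows complete administration of the study drug, and the text does not say whether that means the injections or the one-hour saline. This changes how many events could precede the 60-minute score, and it may cut either way.

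**Conclusion.** The point holds as a cheap improvement to consider. The Safety wording, on its natural reading, ends outcome collection after randomisation for a reason that may be related to fluid volume, and the analysis plan names no set that would keep the patient in. The likely effect on the primary result is small and of unknown direction: 0.2 to 0.9 mm, or 2% to 7% of the 13 mm target, with a false-positive rate of 5.0% to 5.4%. These figures rest on assumed counts (1 or 2 of 45, one arm only, before 60 minutes) and assumed gaps (10 to 20 mm).

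A reader might infer that the primary comparison is seriously compromised, or that the follow-up contact is certain to be lost. The documents support neither.

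**What to change.** **Safety.** Reword so that unblinding a patient does not end data collection. The 30- and 60-minute scores, the chart outcomes and the 24-48 hour contact are still obtained, subject to consent, and scores given after unblinding are marked as such.

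**Data Analysis.** State that all randomised patients are analysed in their assigned arm. Add a sensitivity analysis that leaves out scores given after unblinding, and report unblindings by arm.

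**Cost.** A few sentences in two sections and one mark on the data form, with no new visits, calls or tests; the stated 45 per group is unchanged. The downside is the few self-ratings from patients who know the dose, which is why the sensitivity analysis is included. No change to clinical care, or to when a patient is unblinded, is proposed.

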**The I-FiBH Trial: Intravenous Fluids in Benign Headaches Trial: A Randomized Single
Blinded Clinical Trial**

NCT 03185130

March 15, 2017

INTRODUCTION

Migraine headache has a 1-year period prevalence in the US of 11.7% and accounts for approximately 1.2 million migraine visits to US emergency departments per year [1,2]. There are numerous studies that discuss treatment for migraine and other benign headaches within the emergency department, however, there are very few that discuss specifically the use of intravenous fluids (IVF) for headache treatment [3]. Many of these studies look at various options for treating migraine and other benign headaches: treatment options include dopamine antagonists, opioids, non-steroid anti-inflammatory drugs (NSAIDs), triptans, anti-epileptics and ergot derivatives [2]. Comparisons have been done between many of these treatment options with dopamine antagonists appearing to be the most effective, compared to other treatments [4, 5, 6, 7]. The dopamine antagonist with the most evidence and availability for benign headaches is prochlorperazine [6, 7, 8, 9, 10, 11, 12].

Peripheral IVs and administration are common procedures and treatments within the ED. And while relatively safe, they are not without their own risks [13, 14, 15, 16]. Given that IVF administration is a common part of treatment regimen for benign headache patients in the emergency department and given the lack of randomized trials in adults, we aim to study the use of IVF on pain reduction in headache patients in the adult ED [3]. Given the specific definition of migraine headache, we have chosen to categorize our headaches as benign headaches, avoiding the difficulty of determining if a patient meets the specific criteria for migraine headache [17, 18]. There has been one randomized trial in pediatrics that shows IVF may help in patients with migraines, whereas the adult literature has no randomized control trials and a review of data shows that fluids do not help relieve pain in migraine headache patients [3, 19, 20].

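### The reporting definitions may leave a serious but treatable listed side effect outside both the AE and SAE classes, and the plan does not compare fluid-related harms, AEs or SAEs by arm

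*Combined protocol and SAP*

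**What the plan says.** All references are to the combined protocol and SAP.

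- **Reportable Events, serious events.** There is one criterion: "Serious Adverse Events are those side effects that require Advanced Life Support measures to control symptoms". No other criterion of seriousness appears in the document.
- **Reportable Events, adverse events.** These are "unanticipated side effects that require interventions or anticipated side effects that do not respond to intervention".
- **Reportable Events, exempt events.** Anticipated effects are tied to the manufacturer's "package insert and are treated as routine non-urgent or non-emergent events are not reportable events".
- **Reportable Events, reporting.** "AEs and SAEs will be reported to the IRB within 5 days of the event". No other class is reported.
- **Risk/Benefit.** The prochlorperazine risks end with "tardive dyskinesia, NMS, and blood dyscrasias". The saline risks include "infection, venous thrombosis or phlebitis or hypervolemia".
- **Methods of Measurement.** The form and the 30- and 60-minute assessments cover demographics, headache severity, nausea and vomiting. The 24-48 hour call asks about current headache and pain.
- **Outcome Measures.** The secondary outcomes include admission, nausea, vomiting, additional headache medication and headache resolution.
- **Data Analysis.** The section gives baseline comparisons and a repeated measures ANOVA of the VAS scores. It has no safety analysis.

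**The concern.** Whether an event is reported depends on two things: whether it was expected, and whether it responded to treatment or needed Advanced Life Support. Its consequence for the patient plays no part. A listed effect can put a patient in hospital, respond to ordinary treatment, and on one reading never meet a reportable definition. Several risks that the protocol itself names could take that course.

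The second strand concerns the randomized comparison. Saline volume is the only treatment component that differs between the arms, and the Introduction says of peripheral IVs and their administration that "they are not without their own risks". Yet nothing on the form, in the call, among the outcomes or in the analysis is designed to pick up a harm of the fluid itself. At stake are the completeness of what the IRB sees, in a trial that enrols from age 10, and the ability to set any pain benefit of the bolus against its specific harms.

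**Working it through.** **1. The plan's own figure.** Data Analysis gives an SD of 22 mm, a difference of 13 mm, alpha 0.05 and 80% power; two-sided testing is assumed here. With the normal approximation, n per group = 2 × (1.960 + 0.842)² × 22² / 13² = 2 × 7.849 × 484 / 169 = 44.96, so 45. The stated 45 reproduces. The point does not depend on it, but it sets the scale for any safety table.

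**2. The definitions applied to each kind of event.** The sentence on anticipated effects is ungrammatical and has two readings. In reading A, anticipated means listed on the insert. In reading B, it means listed and also treated as routine.

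| Event | Reading A | Reading B |
|---|---|---|
| Needs Advanced Life Support | SAE, reported | SAE, reported |
| Listed, treated, does not respond | AE, reported | AE, reported |
| Listed, causes admission, treated as more than routine, responds without Advanced Life Support | Neither class | Not anticipated and needed intervention, so AE, reported |
| Listed, treated as routine, responds | Not reportable | Not reportable |
| Not listed, needs intervention | AE, reported | AE, reported |

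The third row is the gap. The exemption does not name such an event, because it was not handled as routine. Under reading A it nevertheless meets neither reportable definition. The shared 5-day rule does not help, because the event belongs to neither class.

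**3. Whether the named risks fall in that row.** This requires that they be on the package insert, which is not in the documents. It is an assumption. A risk that is not on the insert moves to the last row once it needs intervention.

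**4. Whether another part of the plan would catch the event.** Admission is a secondary outcome and inpatients are approached for follow-up, but no cause of admission is recorded. The call does not ask about the infusion site, later care or any side effect. Under Safety, a patient unblinded because of an untoward event leaves the study, so follow-up may end for some patients with harm.

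**5. The contrast between arms.** Under Interventions, one arm receives 5 mL in the hour and the other up to 1000 mL, so the difference is at most 1000 − 5 = 995 mL.

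**6. What a table by arm could show.** The chance of at least one event in 45 patients is 1 − (1 − p)^45. The documents give no event rates, so these are assumed:

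- p = 1%: 36%
- p = 2%: 60%
- p = 5%: 90%

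For a formal comparison of an assumed 5% against 15%, the pooled standard error is √(2 × 0.10 × 0.90 / 45) = 0.0632 and the unpooled one is √((0.0475 + 0.1275) / 45) = 0.0624. Power is Φ((0.10 − 1.96 × 0.0632) / 0.0624) = Φ(−0.384), or 35%. The table can describe harms but not test them.

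**The case against.** The strongest reply is that reading B is natural. NMS or symptomatic hypervolemia leading to admission would hardly be treated as routine, so it would not be anticipated, and it would reach the IRB as an AE within 5 days. This stands as a possible reading. It means that the documents do not support the stronger inference that the rule, as written, keeps serious events from the IRB. What remains is wording with two readings, one of which leaves a gap. Because AEs and SAEs share recipient and deadline, the narrow SAE label alone also changes little; it matters only together with the narrow AE definition.

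Three further inferences are tempting and should not be drawn.

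- **That no side effect is an outcome.** Nausea is listed as a side effect of both drugs and is a secondary outcome. Vomiting and admission are compared too, so some indirect safety information exists.
- **That every named risk bears on the bolus.** Both arms receive an IV line and both drugs, so drug reactions and catheter complications are largely common to the arms. Hypervolemia is the clearest risk tied to volume.
- **That an upper confidence limit for zero events in 45 patients measures the information lost.** Such a limit presumes that every event was recorded. It shows how little even full recording can say about rare harms, not what non-recording costs.

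**Conclusion.** The point holds as a gap that could let a serious event go unreported, not as proof that one would. It rests on two assumptions: that anticipated means listed on the insert, and that the Risk/Benefit risks are on that insert. If either fails, an event that needs intervention is reportable.

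The second strand needs neither assumption. No planned record, outcome or analysis captures or compares fluid-related harms, AEs or SAEs by arm. The plan does not say how often such events are expected, so the number that might be missed cannot be estimated. The primary pain comparison and the sample size are unaffected. This is a worthwhile, inexpensive improvement and not a flaw that undermines the trial.

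**What to change.** 1. Under Reportable Events, define an SAE by what happened to the patient: death, threat to life, admission or prolonged stay because of the event, or lasting harm. Apply it whether or not the event was anticipated and whether or not Advanced Life Support was used. Keep the existing 5-day report.
2. Rewrite the sentence on anticipated effects so that it has one meaning, and reconcile it with the Risk/Benefit list.
3. Add side-effect fields to the data form and side-effect questions to the existing 24-48 hour call, with the reason for any admission.
4. Add to Outcome Measures and Data Analysis a secondary safety outcome: counts of side effects, AEs and SAEs by arm, reported descriptively without significance tests.

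The cost is revised definitions, a few fields, one table and a few more IRB reports. Treatment, sample size and the primary analysis do not change.

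### Nausea and vomiting are secondary outcomes, but the plan states no pre-treatment reading of either, which costs precision and any change-from-baseline analysis

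*Combined protocol and SAP*

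**What the plan says.** Outcome Measures names six secondary outcomes. Nausea and vomiting are two of them: "Secondarily, we will measure the difference between the rates of decline in pain scores, rate of admission, nausea scores, rate of vomiting".

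Methods of Measurement describes the form completed at enrolment as including "age, sex, race, phone number, and baseline headache severity using a 100-mm visual analog scale (VAS"). It then gives the later schedule: "Repeat headache severity scores will be measured at 30 and 60 minutes". It defines the clock: "Time zero begins immediately after complete administration of the study drug". Finally it places nausea and vomiting: "Nausea (with a 100 mm VAS) and vomiting will also be assessed at these time intervals".

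Data Analysis lists baseline comparability tests on gender, race and age, and "a chi (with Yates correction)-squared test on severity of presenting headache, to determine if they are similar". Nausea is not among them. The same section sends the VAS measurements to a repeated measures ANOVA, without separating pain from nausea and without naming a baseline covariate.

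**The concern.** Headache has an explicit baseline value, and nausea and vomiting do not. Staff who follow the text as written could reasonably record nausea for the first time 30 minutes after time zero. A patient who arrived very nauseated and one who arrived with none would then enter the comparison with nothing to tell them apart.

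Three things are at stake.

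- **Precision.** The trial takes all benign headache, not only migraine, so presenting nausea may vary widely. Without a baseline value, that variation stays in the error term.
- **Change over time.** With values at 30 and 60 minutes only, the group-by-time term of a repeated measures ANOVA of nausea describes only the second half hour. Any change from arrival is out of reach. So is the distinction, within a patient, between nausea that persisted and nausea that began after treatment. The Risk/Benefit section lists nausea as a side effect of both prochlorperazine and diphenhydramine.
- **Balance.** Allocation is by simple randomisation, with separate lists only for the pediatric and adult EDs. A chance difference in presenting nausea could be neither seen nor adjusted for.

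A baseline reading that is not taken before treatment cannot be recovered afterwards.

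**Working it through.** **1. The plan's own figure.** From Data Analysis: SD 22 mm, difference 13 mm, 80% power, alpha 0.05 (taken as two-sided).

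n per group = 2 × (1.960 + 0.842)² × 22² / 13² = 44.96, so 45. This reproduces the stated figure under the normal approximation. It concerns pain only, and nothing below changes it.

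**2. Is a pre-treatment nausea reading stated anywhere?**

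| Item | Headache | Nausea and vomiting |
|---|---|---|
| Listed on the enrolment form | yes | no |
| Called baseline in the text | yes | no |
| Scheduled at 30 and 60 min | yes | yes, on the natural reading |
| In the baseline comparability tests | yes | no |

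No section states one.

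**3. Possible chance imbalance at arrival.** The documents give no nausea SD, so the SDs here are assumptions; 22 mm is borrowed from pain. With 45 per arm, the SE of the difference in baseline means is SD × √(2/45).

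- SD 22 mm: SE 4.6 mm, 95% range ±9.1 mm
- SD 30 mm: SE 6.3 mm, 95% range ±12.4 mm

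If half of patients are nauseated at arrival (assumed), the difference in proportions has SD √(2 × 0.25 / 45) = 0.105, a 95% range of about ±21 percentage points.

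**4. How much of that reaches the outcome.** With equal SDs at baseline and follow-up, an imbalance carries forward multiplied by the correlation r.

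- SD 22 mm: ±9.1 × 0.3, 0.5, 0.7 = ±2.7, ±4.6, ±6.4 mm
- SD 30 mm: ±12.4 × 0.3, 0.5, 0.7 = ±3.7, ±6.2, ±8.7 mm

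This is part of the ordinary sampling error of the unadjusted comparison, not an addition to it.

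**5. What a baseline covariate would gain.** Residual variance becomes (1 − r²) times the unadjusted variance. The smallest difference detectable with 80% power is (1.960 + 0.842) × SD × √(1 − r²) × √(2/45). The unadjusted sample size that would give the same precision is 45 / (1 − r²).

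| r (assumed) | Variance removed | Equivalent n per arm | Detectable difference, SD 22 | Detectable difference, SD 30 |
|---|---|---|---|---|
| no adjustment | – | 45 | 13.0 mm | 17.7 mm |
| 0.3 | 9% | about 49 | 12.4 mm | 16.9 mm |
| 0.5 | 25% | 60 | 11.3 mm | 15.3 mm |
| 0.7 | 49% | about 88 | 9.3 mm | 12.7 mm |

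**The case against.** **The text may intend a baseline reading.** The form is described by what it is to include, which need not be a full list, and the form itself is not in the documents. The word *also* ties nausea to the headache schedule, and that schedule does have a baseline. This stands as far as it goes: a reader might infer that the sponsor deliberately left out baseline nausea, and the documents do not establish that. They show only that the reading is not stated, and that the nearest stated measurement times are 30 and 60 minutes.

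**A time-zero reading might serve.** Under Interventions, both arms receive diphenhydramine and then prochlorperazine before the saline is connected. If the study drug that sets time zero means those two medicines, a score at time zero would precede the randomised contrast and could be used as a covariate. The documents do not settle what the term covers. No time-zero nausea score is clearly scheduled, and one taken then would not describe nausea at arrival.

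**The comparison is valid without a baseline.** This stands in full. A reader might infer that a chance imbalance in presenting nausea would bias the result, or would pass for an effect of fluid. The documents do not support that. Randomisation keeps the comparison unbiased in expectation, and the standard error already allows for chance imbalance. Nor does the whole baseline imbalance reach the outcome; only about r times it does. Outcome Measures asks for nausea scores, not their decline, so a comparison of later scores answers the stated question. The absence of nausea from the comparability tests adds little, since significance tests of baseline balance are not needed for validity.

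**Conclusion.** The point holds as a modest, inexpensive improvement to two secondary outcomes. The plan states no pre-treatment reading of nausea or vomiting, and on the natural reading none is taken. The comparison between arms remains valid, and the primary outcome and its 45 per group are untouched.

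The loss is in precision, in any change-from-baseline analysis, and in the ability to see or adjust for chance imbalance. Its size depends on a correlation that the documents do not give. It is small at r = 0.3 (9% of residual variance) and material at r = 0.7 (49%). The detectable differences in millimetres rest further on an assumed nausea SD of 22 or 30 mm. If the sponsor already intends a baseline reading, only the wording needs to change.

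**What to change.** 1. Add the 100-mm nausea VAS and a yes/no item for vomiting with this headache episode to the baseline form, completed with the headache VAS before any study drug is given.
2. In Methods of Measurement, replace the reference to time intervals with the words *at baseline, 30 and 60 minutes*.
3. In Data Analysis, state that nausea scores at 30 and 60 minutes are compared between arms with baseline nausea as a covariate, and that vomiting is reported alongside baseline vomiting status.

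The cost is one VAS line and one tick box on an existing form, a few seconds per patient, a one-sentence change to the measurement schedule and a line in the analysis section. It needs no extra visit or staff and no change to the sample size.
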